## Analysis plan

**AIM 1 Comparative Effectiveness: Main Effects:** Within five clinically important schizophrenia subgroups, compare the effectiveness and safety of alternative medication strategies beyond antipsychotic monotherapy.

We will construct Cox models to estimate effects of the study treatments. We will first examine unadjusted treatment effects and then will conduct analyses using basic adjustment for demographic factors. Then we will construct Cox models using weighted propensity scores. Follow-up time will be censored at discontinuation or change of second drugs, death, or loss of Medicaid.

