### Secondary

We will also investigate time to index treatment discontinuation, time to introduction of another psychotropic medication, psychiatric emergency department visits, all-cause hospitalization, and death.

We will investigate adverse effects of medications including incidence of major cardiovascular events and diabetes mellitus.

Outcomes	
Death	Date of death will be defined by the Social Security Death Master File.
Psychiatric Hospitalization	Hospital claims will define inpatient admissions with a first listed mental disorder diagnosis (ICD-9:290-310). High levels of agreement between diagnoses in inpatient medical records and inpatient claims have been reported for several mental disorder groups, including schizophrenia (100.0%), major mood disorders (98.7%), alcohol dependence (97.8%), and drug dependence (96.4%). 
Psychiatric ED Visits	Emergency department claims are a reliable source of diagnostic information in relation to medical records and a valid source of illness severity information.  Emergency department visits in which the first listed diagnosis is a mental disorder (ICD-9-CM: 290-319) will be defined as emergency department mental health visits.
Self-Injurious Behavior	Deliberate self-harm will be defined by an E-code of E950-E958, excluding late effects of deliberate self-harm (E959), on any inpatient, emergency department, or outpatient claim. High positive predictive values have been reported. 
Diabetes Mellitus	One or more claims with a physician diagnosis of diabetes will define diabetes mellitus. Using self-reported diabetes status as the criterion standard, $\geq 1$ physician claim with any diagnosis of diabetes or a diabetes complication (ICD-9 codes: 295.00-2950.93, 357.2, 362.0-362.02, 366.41) has acceptable sensitivity (68.5%) and specificity (96.9%), and (kappa=0.76).  Sensitivity of 90% and specificity of 93% with self-reported diabetes. 
Cardiovascular Events:	Acute myocardial infarction (AMI) (ICD-9-CM: 410) or stroke (430-438, except 435) will be defined by diagnostic codes on inpatient claims of $\geq 3$ days in duration.  With this AMI definition 75% met criteria for definite or probable AMI on independent review of cardiac biomarkers, electrocardiograms, presenting symptoms, and medical history, and an additional 12% had a suspected AMI. 

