## Follow-up and censoring

Follow-up will begin at the date of new treatment initiation (t0 or index date) and will end after 365 days regardless of changes in pharmacotherapy (intent-to-treat approach). We will also conduct secondary analyses using a 180-day follow-up period and an as-treated specification. In the as-treated approach, follow-up will end at discontinuation of the new treatment ( $>10$  days without drug) or addition of another psychotropic agent (antipsychotic, mood stabilizer, antidepressant, or benzodiazepine). All analyses will be censored at loss of Medicaid (because that is the data source) with one exception—in intent-to-treat mortality analyses, follow-up will not be censored at loss of Medicaid because date of death data comes from the Social Security Master File, not Medicaid.

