### *Propensity score estimation and application*

Propensity score methods involve two steps: estimation of the propensity scores and application of the propensity score. Estimation of the propensity scores involves decisions about which covariates to include in the prediction model of the propensity scores and what form the model should take. We will use expert opinion to select the variables to include in the propensity score. To estimate the propensity scores we will first use logistic regression including all baseline predictors occurring prior to treatment assignment. In addition, we will augment our analysis with another non-parametric method for building the propensity score model such as a generalized boosting algorithm implemented with regression trees. We will assess the sensitivity of our results to the choice of the propensity score model.

For the application of the propensity scores, we will use weighting by the odds to estimate the average treatment effect on the treated sample and weighting by the inverse probability of treatment weights to estimate the average treatment effect in the population.

We will examine the covariate balance using standardized differences in covariate means across the treatment groups after weighting, and address any significant imbalances.

**AIM 2 Heterogeneity of Treatment Effects:** Within the five subgroups, explore whether the comparative effectiveness and safety of alternative treatment strategies varies according to patient age and presence of a substance use disorder.

We will use similar Cox model techniques for the HTE analyses. First we will assess interaction of age and substance use variables with treatment. If such interactions are found, we will then perform analyses examining alternative treatment strategies stratified by age group or substance use.

The rationale for investigating patient age as a moderator of antipsychotic treatment effects follows from evidence that individuals early in the course of psychosis may respond differently to medications than people with more chronic illness. The rationale for investigating comorbid diagnosis of a substance use disorder as a moderator of treatment effects follows from evidence that people diagnosed with schizophrenia and comorbid substance use disorders respond more poorly to antipsychotic medications than those without comorbid substance use disorders.

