### Sensitivity Analyses

We will conduct sensitivity analyses to confirm findings from the primary analyses and to examine their generalizability. In addition to the primary 360-day intention-to-treat analyses we will conduct 180-day intention-to-treat analyses and as-treated analyses. Another sensitivity analysis will examine subgroups of people with depression, anxiety, or mania diagnoses that are listed by more than one provider.

**Quantitative Sensitivity Analyses for Unmeasured Confounders.** Because the observed relative risk is a closed-form function of the balance of confounders among exposure groups, the strength of the confounder, and the prevalence of the confounder, it is possible to estimate the extent of unmeasured and thus unadjusted confounding necessary to fully explain the observed findings, i.e., would move the observed relative risk to statistical insignificance (the null).

To quantify how strong unmeasured confounding would have to be to explain the observed effect sizes among our comparison groups, we will use the array approach to understand how the strength of unmeasured confounders with known associations with our outcomes, such as BMI and risk of diabetes, and the confounder imbalance among study groups might affect the observed relative risk.

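### The censoring sentence for the Aim 1 Cox models is in substance as-treated and contradicts the intent-to-treat primary analysis set elsewhere in the plan

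*Combined protocol and SAP*

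**What the plan says.** The Analysis plan, under Aim 1 (main effects), describes unadjusted, demographically adjusted and propensity-weighted Cox models. It then gives one censoring sentence: "Follow-up time will be censored at discontinuation or change of second drugs, death, or loss of Medicaid". It does not restrict that sentence to any one analysis, mention intent-to-treat, give a 365-day end or refer back to the section on follow-up.

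Three statements elsewhere bear on the same models:

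- Follow-up and censoring says that follow-up "will end after 365 days regardless of changes in pharmacotherapy (intent-to-treat approach").
- The same section continues: "We will also conduct secondary analyses using a 180-day follow-up period and an as-treated specification". It defines the second of these: "In the as-treated approach, follow-up will end at discontinuation of the new treatment" (more than 10 days without drug) or when another psychotropic is added.
- Sensitivity Analyses says: "In addition to the primary 360-day intention-to-treat analyses we will conduct 180-day intention-to-treat analyses and as-treated analyses".

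The primary outcome is time to psychiatric hospitalization. Aim 2 takes over the Aim 1 Cox approach, so the Aim 1 sentence reaches it too.

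**The concern.** A Cox model cannot both ignore drug changes and censor at them. The sentence that does the second sits in the only section that specifies the Aim 1 models, which is where an analyst would look when programming them. The plan states no order of precedence between sections.

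The choice decides what the primary hazard ratio means. Under intent-to-treat it compares admission over a year by the strategy started. Under the Aim 1 sentence it compares admission only while the started drug continues unchanged. The second version counts fewer admissions. It is also open to informative censoring if patients who stop differ in admission risk from those who continue: the propensity model is "logistic regression including all baseline predictors occurring prior to treatment assignment", and no weights for censoring are described.

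**Working it through.** **Step 1. The rules side by side (primary outcome).**

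| | Follow-up and censoring (main rule) | Sensitivity Analyses | Aim 1 sentence |
|---|---|---|---|
| Status | intent-to-treat; as-treated secondary | intention-to-treat primary; as-treated additional | unqualified, under main effects |
| Ends at drug stop or change? | no | no (intention-to-treat) | yes |
| Ends at loss of Medicaid? | yes, except intent-to-treat mortality | not stated | yes |
| Fixed end | 365 days | 360 days | none given |

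For hospitalization, the conflict lies in the drug stop or change. Loss of Medicaid agrees with the main rule, and censoring at death is compatible with intent-to-treat. The Aim 1 wording is not identical to the as-treated definition, since it says *change* of second drugs and not *addition* of another psychotropic. Hence 'in substance' as-treated.

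**Step 2. Which rule the rest of the plan assumes.** The instrumental variable section compares its results with intention-to-treat estimates. The Sample size section claims at least 80% power for a 5.0-point difference in 1-year admission with 1,534 patients per group (0.70 × 2,192 = 1,534.4), two-sided 0.05. No base rate is given. The usual formula is

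power = Φ{[|p1 − p2|√n − 1.96√(2p̄(1 − p̄))] / √(p1(1 − p1) + p2(1 − p2))}.

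With the least favourable rates, 47.5% v 52.5%: (0.05 × 39.17 − 1.96 × 0.7071) / 0.7062 = 0.81, so power is 79.1%. At 30% v 35% it is 84.1%, and at 20% v 25% it is 91.3%. The stated figure therefore reproduces on a full year of follow-up, which fits intent-to-treat and not a model censored at drug changes.

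**Step 3. Can the consequence be sized?** Not from the plan. The illustration below shows why even the direction for power is open. All inputs except n = 1,534 are assumed: 1-year risks 25% v 30%, constant hazards, and stopping unrelated to risk and equal in both arms.

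- Yearly hazards: λ1 = −ln 0.75 = 0.288 and λ2 = −ln 0.70 = 0.357; hazard ratio 0.288/0.357 = 0.81.
- Events over 365 days: 1,534 × (0.25 + 0.30) = 844.
- Events under the Aim 1 sentence, per arm: n·λ/(λ + δ)·(1 − e^−(λ+δ)), with δ = ln 2 × 365/median persistence. For a median of 180 days, δ = 1.406, giving 213 + 257 = 470.
- Power (Schoenfeld): Φ(√D·|ln HR|/2 − 1.96).
- If the effect ends at stopping, the index hazard returns to λ2. The intent-to-treat hazard ratio then solves the population Cox score equation, with 903, 895, 880 and 865 events.

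| Median persistence (days) | Events, Aim 1 sentence | Power, Aim 1 sentence (HR 0.81) | Intent-to-treat, effect persists (HR 0.81, 844 events) | Intent-to-treat, effect ends at stopping: HR; power |
|---|---|---|---|---|
| 60 | 215 | 35% | 88% | 0.95; 12% |
| 90 | 301 | 46% | 88% | 0.93; 19% |
| 180 | 470 | 64% | 88% | 0.89; 40% |
| 365 | 620 | 76% | 88% | 0.86; 62% |

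The pattern holds at other assumed risks. With a 180-day median, 15% v 20% gives 78% under the Aim 1 sentence against 96% or 50% under intent-to-treat; 40% v 45% gives 57% against 81% or 36%. Fewer events are counted throughout, but power can be lower or higher, and the two rules estimate the same hazard ratio only if the effect outlasts treatment. The illustration uses the plan's 1:1 matched example and not the weighted Cox models, so it is not a power statement for the planned analysis.

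**The case against.** The strongest reply is that the plan answers the question elsewhere. A section devoted to follow-up and censoring sets intent-to-treat as the main rule, Sensitivity Analyses labels it primary, and both analyses are planned anyway. That stands, and it limits the severity. It does not remove the conflict: nothing confines the Aim 1 sentence to the as-treated analysis, and it directly follows the main models.

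A reader might go further in three ways that the documents do not support.

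- *The primary hazard ratio will be as-treated.* The weight of the text points the other way, and the Aim 1 sentence never calls itself primary.
- *The study is biased or underpowered because of this.* That would need the sentence to be applied to the main model, plus persistence, admission rates and a link between stopping and risk that the plan does not give. The lack of censoring weights also bears on the planned secondary as-treated analysis and is a separate matter.
- *The sentence also breaks the mortality and secondary analyses.* Follow-up and censoring states an express exception, "in intent-to-treat mortality analyses, follow-up will not be censored at loss of Medicaid", and a specific exception ordinarily governs a general sentence. For outcomes such as "time to index treatment discontinuation, time to introduction of another psychotropic medication", ordinary practice counts the outcome as the event. These are drafting points that the corrected sentence can absorb.

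**Conclusion.** Wrong as written. The Aim 1 sentence and the 365-day intent-to-treat rule cannot both govern the same model. The sentence is probably leftover wording; that is an inference from the four places that point to intent-to-treat (Follow-up and censoring, the instrumental variable section, Sensitivity Analyses and Sample size). If those are followed, the primary result is unchanged. If the sentence were followed, the primary hazard ratio would answer a different question, rest on fewer events than the 1-year basis of the power calculation, and be exposed to informative censoring. The size and direction of any effect on bias or power are not quantifiable from the documents. This is a consistency correction to the main-model rule that should be made; it is not evidence of a flawed primary analysis.

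**What to change.** Replace the Aim 1 censoring sentence with wording such as:

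> The primary intent-to-treat Cox models follow each patient for 365 days whether or not drug treatment changes. They are censored at death (unless death is the outcome) and at loss of Medicaid (except in the intent-to-treat mortality analyses). Censoring at discontinuation or when another psychotropic is added, as defined in Follow-up and censoring, applies only to the secondary as-treated analyses.

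Also state whether *change of second drugs* in the Aim 1 text means the same as the addition of another psychotropic in Follow-up and censoring, and reconcile 360 days in Sensitivity Analyses with 365 days in Follow-up and censoring.

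The cost is wording in the protocol and SAP only. No new data or analysis is needed.

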### *Propensity score estimation and application*

Propensity score methods involve two steps: estimation of the propensity scores and application of the propensity score. Estimation of the propensity scores involves decisions about which covariates to include in the prediction model of the propensity scores and what form the model should take. We will use expert opinion to select the variables to include in the propensity score. To estimate the propensity scores we will first use logistic regression including all baseline predictors occurring prior to treatment assignment. In addition, we will augment our analysis with another non-parametric method for building the propensity score model such as a generalized boosting algorithm implemented with regression trees. We will assess the sensitivity of our results to the choice of the propensity score model.

For the application of the propensity scores, we will use weighting by the odds to estimate the average treatment effect on the treated sample and weighting by the inverse probability of treatment weights to estimate the average treatment effect in the population.

We will examine the covariate balance using standardized differences in covariate means across the treatment groups after weighting, and address any significant imbalances.

**AIM 2 Heterogeneity of Treatment Effects:** Within the five subgroups, explore whether the comparative effectiveness and safety of alternative treatment strategies varies according to patient age and presence of a substance use disorder.

We will use similar Cox model techniques for the HTE analyses. First we will assess interaction of age and substance use variables with treatment. If such interactions are found, we will then perform analyses examining alternative treatment strategies stratified by age group or substance use.

The rationale for investigating patient age as a moderator of antipsychotic treatment effects follows from evidence that individuals early in the course of psychosis may respond differently to medications than people with more chronic illness. The rationale for investigating comorbid diagnosis of a substance use disorder as a moderator of treatment effects follows from evidence that people diagnosed with schizophrenia and comorbid substance use disorders respond more poorly to antipsychotic medications than those without comorbid substance use disorders.

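### Aim 2 specifies no propensity score or balance check within age and substance-use strata, so treatment selection that differs by stratum could create or hide heterogeneity

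*Combined protocol and SAP*

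**What the plan says.** Aim 1 fits unadjusted and demographically adjusted Cox models. "Then we will construct Cox models using weighted propensity scores" (Analysis plan, AIM 1). The section on propensity score estimation and application describes the score: "To estimate the propensity scores we will first use logistic regression including all baseline predictors occurring prior to treatment assignment". It adds a second, non-parametric score, for example a "generalized boosting algorithm implemented with regression trees", and plans to compare results across score models. The weights are odds weights for the effect in the treated and, for the population effect, "weighting by the inverse probability of treatment weights to estimate the average treatment effect in the population". The balance diagnostic is this: "We will examine the covariate balance using standardized differences in covariate means across the treatment groups after weighting", with significant imbalances to be addressed.

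Aim 2 is then set out in three sentences. The opening one refers back to the Aim 1 modelling: "We will use similar Cox model techniques for the HTE analyses". The next names a test of the two moderators as the initial step. The last makes the stratum-level work depend on that test: "If such interactions are found, we will then perform analyses examining alternative treatment strategies stratified by age group or substance use".

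Appendix 2 lists substance use disorder as one covariate of the score and age as 12 bands. Nothing says whether the score is re-estimated, or balance re-checked, within substance-use or age strata.

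**The concern.** A score that is adequate for an average effect need not be adequate for a contrast between strata. Suppose prior admissions steer prescribers towards one drug class in patients without a substance use disorder, but less so, or the other way, in patients with one. A logistic score with main effects only finds a compromise coefficient. Weighted means of prior admissions then agree across the treatment groups as a whole, yet one stratum is under-corrected and the other over-corrected. The treatment-by-moderator coefficient picks up that residual confounding.

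Two errors can follow. A homogeneous effect can be reported as heterogeneous. Or bias running against a real difference can cancel it; because stratified analyses follow only when an interaction is found, the stratum estimates where the problem might be noticed would then not be produced. Aim 2 is meant to inform treatment choice by age and substance use, so either error matters. Sample size gives no protection: the bias stays fixed while the standard error shrinks.

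**Working it through.** **The plan's own figure.** The documents give no figure for Aim 2 or for within-stratum balance. The nearest is an Aim 1 figure in the Sample size section: at least 80% power for a 5.0-point difference with 1,534 patients per group. No event rate is stated. A pooled two-proportion test gives 79.1% at an average rate of 50%, 80.7% at 40% and 89.3% at 25%, so it reproduces. It says nothing for or against this point.

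**Inputs, all assumed because the documents do not give them.** S = substance use (35%). X = a binary prognostic covariate (40%, independent of S). Reference one-year risk 25%. X multiplies the hazard by 2.5 and S by 1.3. Treatment has no effect in either stratum.

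**Formulas (population calculation, no sampling error).**
- True selection: logit P(T=1) = −0.2 + 0.2·S + ln(OR₀)·X + [ln(OR₁) − ln(OR₀)]·S·X, where OR₀ and OR₁ are the X–treatment odds ratios without and with substance use.
- Fitted score e: logistic on S and X only. Weights are 1/e (treated) and 1/(1−e) (comparator).
- Hazard: λ₀·2.5^X·1.3^S, with λ₀ = −ln(1 − 0.25) = 0.288.
- Standardized difference: weighted mean of X in treated minus comparator, divided by √(0.4 × 0.6) = 0.490.
- The hazard ratio (HR) in each stratum is the root of the weighted Cox score equation over one year. False ratio = HR(S=1)/HR(S=0).

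| OR₀, OR₁ | Std. diff. overall | S=0 | S=1 | HR, S=0 | HR, S=1 | False ratio |
|---|---|---|---|---|---|---|
| 1.5, 1.5 | 0.00 | 0.00 | 0.00 | 1.000 | 1.000 | 1.000 |
| 1.5, 1.25 | 0.00 | +0.03 | −0.06 | 1.014 | 0.974 | 0.960 |
| 1.5, 1.0 | 0.00 | +0.07 | −0.13 | 1.032 | 0.943 | 0.914 |
| 1.22, 1/1.22 | 0.00 | +0.07 | −0.13 | 1.032 | 0.944 | 0.915 |
| 1.5, 1/1.5 | 0.00 | +0.14 | −0.26 | 1.065 | 0.890 | 0.836 |

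The third and fourth rows nearly coincide, since 1.0/1.5 = 0.67 and (1/1.22)/1.22 = 0.67. The size therefore depends on how far the odds ratios differ between strata and does not require a change of sign. With a weaker confounder (hazard ratio 1.5) the second row becomes 0.98 and the third 0.96. Varying the prevalence of X from 30% to 50% leaves the last row at 0.84 to 0.85. Adding the S·X term to the score returns every row to 0.00 within strata and a ratio of 1.00.

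**Effect on the interaction test.** A second set of assumptions: 30% substance use, X doubling the hazard, S·X log-odds −0.5 (stratum odds ratios e^0.25 = 1.28 and e^−0.25 = 0.78). The false ratio is 0.919, so ln = −0.084. Take 70% of the Table 5 episodes as distinct patients, antidepressant versus second antipsychotic, and an assumed 25% event rate. For uncomplicated schizophrenia, events are 0.7 × 27,005 × 0.25 = 4,726 and 0.7 × 25,061 × 0.25 = 4,386. The variance is (1/4,726 + 1/4,386) × (1/0.3 + 1/0.7) = 0.0021, the standard error 0.046, and z = 0.084/0.046 ≈ 1.85. A nominal 5% test then rejects about 45% of the time. The same steps give 17% in schizoaffective disorder, 10% in depression and 6% in anxiety. With S·X = −1.0 the rates are 96%, 51%, 24% and 10%. Variance inflation from weighting is ignored, so these rates are approximate and probably somewhat high.

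**The case against.** A reader might infer that Aim 2 carries the Aim 1 weights over unchanged. The text does not say so: similar techniques are compatible with re-estimation, and for the stratified second step re-estimation within strata is a natural reading. What stands against the plan is that both readings comply with it, and that the only score form and balance check it describes are for whole treatment groups.

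A reader might also infer that the bias is automatic. It is not. It needs selection on a prognostic covariate to differ by moderator, and nothing in the documents shows that it does. The 0.84 to 0.85 case is extreme. With odds ratios of 1.5 and 1.25 the ratio is 0.96, and the stratum differences already fall below the customary 0.1.

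The boosted-tree score is a fair counterargument. Trees can capture moderator-by-covariate interactions, and the plan will compare results across score models. That protection is partial: the model is an addition to the logistic score, and its balance is also assessed only across whole treatment groups. A balance table that happened to include the product of moderator and covariate would expose the problem (a standardized difference of about −0.15 in the S·X = −1.0 scenario), but no such row is planned.

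Finally, Aim 2 is exploratory, and in anxiety and depression the moderate scenario barely moves the error rate above 5%. That is true; the exposure is greatest in the two largest subgroups.

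**Conclusion.** The concern holds as a gap with a cheap remedy. The score and balance check described for Aim 1 do not secure balance within the strata that Aim 2 compares, and Aim 2 adds nothing to them. If selection differs by substance use or age, the interaction test can show heterogeneity that is not there or miss heterogeneity that is. Under the assumed inputs the false ratio of hazard ratios runs from 1.00 through about 0.96 and 0.91 to 0.84 to 0.85 at the extreme. The prevalences, hazard ratios and odds ratios are all illustrative, so the range shows what could happen and does not predict what this study will find. The documents do not support saying that weights are reused, that bias will occur, or that 0.85 is typical.

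**What to change.** In the Aim 2 section, state that the propensity score for the heterogeneity analyses is either estimated separately within substance-use strata and a few broad age groups, or fitted with moderator-by-covariate terms. The 12 age bands in Appendix 2 are too fine for separate models: 611 anxiety episodes on a second antipsychotic over 12 bands is about 51 per band.

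Report standardized differences within each stratum, with 0.1 as a guide and not a hard requirement, and address imbalances there before fitting the interaction. Apply the same within-stratum check to the boosted-tree score. Report stratum-specific estimates with confidence intervals alongside the interaction test, whatever its result.

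No new data are needed. The cost is more analysis runs and wider intervals in small strata such as anxiety.
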